# Feasibility testing: Pilot RCT (patient component)

After SweetMama is modified based the usability testing phase and provider feedback, which we anticipate will take 1-2 months, feasibility testing will occur with up to 50 eligible pregnant women via field testing. The goals of this phase are to field test recruitment, retention, and assessment strategies, as well as delivery of SweetMama within a pilot RCT, to assess feasibility and inform the design of a full trial assessing behavior, glycemic control, and perinatal outcomes. We will collect feasibility data regarding recruitment, technical challenges, quality assurance, and retention, as well as clinical outcomes data and patient-reported outcomes.

Women will be recruited to participate in the same manner as described above, via routine clinical interactions. Medical records will be reviewed for eligibility and women with diabetes will then be approached for verbal in-person screening and recruitment using a recruitment script (Appendix E). Participants will sign written informed consent. Enrolled women will be provided a "SweetMama timeline" document that explains the study activities, provides contact information, and outlines how to contact the team for technical help or any other needs. We will then randomized participants. Randomization, via REDCap, 76 will be unbalanced to

offer greater odds of receiving the experimental treatment in order to enhance the research team's experience with SweetMama and incentivize participation, with a target sample of 40 (randomized 1:3, stratified by DM type). The target sample size is 40, but up to 50 women may be enrolled in order to account for drop-out or the requirements of the randomization schema.

Women who are randomized to usual care will receive no orientation to or enrollment in SweetMama. They will receive surveys at enrollment, during the delivery hospitalization, and at the postpartum visit (see details in table below). Women who receive usual care will not undergo interviews.

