The primary outcomes of Aim 2 are feasibility (≥80% retention; see below) and satisfaction (USE, SUS, interviews). Secondary outcomes are behavioral (DES-SF, PAM, adherence), clinical (hypertensive disorders, delivery mode, birthweight, neonatal hypoglycemia, NICU admission), and glycemic control outcomes. Glycemic control will be assessed as hemoglobin A1c (final and difference from enrollment to delivery) and as proportion of blood glucose measures out of goal. Adherence will be assessed as proportion of prenatal visits attended and with available glucose data.

In order to assess these outcomes, the measures in the following table will be collected via the medical record, user interaction reports, and patient report:

All women		Additional data gathered in SweetMama arm	
Baseline	
 
Demographics, clinical data, eHEALS, NVS, DES- SF, PAM, technology comfort questionnaire
 
		
Monthly	
 
Retention (continuation in care and the study protocol)
 
	
 
SweetMama retention and adoption
 
SweetMama functionality, quality assurance & content feedback (technical check-ins)
 
	
Delivery	
 
Retention (continuation in care and the study protocol)
 
	
 
SweetMama functionality, quality assurance, & content feedback
 
Exit interview- feasibility, improvement, and engagement
 
	

	Treatment adherence		•	Satisfaction and usability: USE and SUS
	•	Behavioral measures: DES-SF, PAM	•	User interaction data (see Aim 1)
	•	Maternal and neonatal clinical data		
Postpartum	•	Behavioral measures: DES-SF, PAM	
 
Exit interview part 2 – postpartum curriculum - feasibility,
 
	
				improvement, and engagement

As in the usability testing phase, we will collect baseline information on (see details above):

- Demographic and clinical characteristics
- Electronic health literacy measured the eHealth Literacy Scale (eHEALS)65
- Health literacy measured via the Newest Vital Sign
- Diabetes self-efficacy measured via the Diabetes Empowerment Scale–Short Form (DES-SF
- Patient activation measured via the Patient Activation Measure (PAM)
- Technology comfort Using a modified version of the Technology Comfort Questionnaire (12 items), we will ask about smartphone familiarity and comfort.

We will also collect data from study and medical record upon completion on:

- Retention, measured as continuation in the study protocol

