Sample size calculation: As this study is not a hypothesis-testing study but rather a usability/feasibility study, the sample size is not based on a statistical power calculation but on standard sample sizes for studies of this nature. Sample sizes were generated based on data illustrating that these sizes are sufficient to inform high quality user-centered design of a larger scale, next step behavioral intervention trial. For the pilot RCT phase, the sample size is set to provide sufficient data to make reasonable estimates regarding recruitment and feasibility but is not designed to assess clinical outcomes.

Analysis: This is a mixed methods analysis. Descriptive statistics using bivariable analysis will be used to characterize the study populations. For statistical comparisons, all tests will be two sided and p<0.05 will be considered statistically significant. All statistics will be performed using STATA 15. Analyses will be performed as follows:

- Focus groups and user interviews (including provider focus groups and interviews): During focus groups and user interviews, we will take detailed notes and audio record in order to capture participant feedback. After each group, the research team will construct a brief preliminary summary report. Transcripts will then undergo rigorous and reproducible qualitative analysis techniques using the constant comparison method. Analysis will be performed in Dedoose, a secure qualitative data management and analysis software that facilitates collaborative exploration of data and identification of themes in accordance with the Health Belief Model and Theory of Self-Efficacy. Dedoose has been previously used for multiple studies performed in our Department and has data security approvals by NUIT; only deidentified data will be uploaded to Dedoose. We will ensure reproducible and rigorous interpretations are accomplished via use of memos, creation of a consensus code list with clear operational definitions, and calculation of agreement statistics for inter-coder reliability. The final report will compare data gathered from focus groups and user interviews and summarize themes. We will then iteratively modify SweetMama based on these results.

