  - O Quantitative: Using Stata, we will report baseline characteristics, recruitment and retention metrics (cumulatively and per month), and user interaction data. Outcomes will be compared a) within individuals (baseline vs. postpartum) and b) between groups (retention, behavioral measures and clinical outcomes). Bivariable analyses will be performed, with *a priori* subgroup analyses to assess differences by age, diabetes type, medication use/changes, and gestational age at entry (<20 weeks vs. ≥20 weeks). Regression modeling will be used to assess the relationship of SweetMama use to retention and other behavioral outcomes after controlling for potential confounders, such as length of exposure. Within the experimental group, although statistical power will be limited, we will also perform bivariable and multivariable analyses to assess relationships between user clinical/behavioral characteristics and satisfaction and use. Feasibility targets for study retention will be set at 80% retention in the study protocol. Feasibility target for SweetMama adoption will be 80% active use (defined as at least weekly interaction with SweetMama content). Targets are set at 80% based on prior literature using this threshold to represent greater engagement. 36,61

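### The pilot's baseline-to-postpartum test within individuals is uncontrolled and cannot support a statement about SweetMama; the plan should rest such statements on a baseline-adjusted between-arm difference

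*Combined protocol and SAP*

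**What the plan says.** The point concerns the protocol version that includes the pilot RCT.

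- **Comparisons.** Under Data and Specimen Management (Analysis, Pilot RCT phase, Quantitative): "Outcomes will be compared a) within individuals (baseline vs. postpartum) and b) between groups (retention, behavioral measures and clinical outcomes". Regression modeling of retention and other behavioral outcomes follows, controlling for potential confounders. Length of exposure is the only confounder named.
- **Significance rule.** The opening of the same Analysis text: "For statistical comparisons, all tests will be two sided and p<0.05 will be considered statistically significant".
- **Allocation.** Under Feasibility testing: Pilot RCT (patient component), randomization is unbalanced to "offer greater odds of receiving the experimental treatment", "with a target sample of 40 (randomized 1:3, stratified by DM type". The same section adds that "up to 50 women may be enrolled in order to account for drop-out or the requirements of the randomization schema".
- **Outcomes concerned.** The measures table in that section lists DES-SF and PAM for all women at baseline, and "Behavioral measures: DES-SF, PAM" again at delivery and postpartum. Both are secondary outcomes. The primary outcomes are retention and satisfaction.
- **Purpose.** The sample size paragraph says that the study does not test hypotheses and that the pilot is not sized for clinical outcomes. It gives no effect size or SD.

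The text does not say which group the within-individual comparison is run in, or which comparison carries the inference. It names no baseline score as a covariate for the behavioral measures.

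**The concern.** A randomised trial has a control arm so that change over time can be separated from the effect of the intervention. A baseline-to-postpartum test discards that control. The Background says that diabetes care in pregnancy itself calls for patient education and engagement, so self-efficacy and activation could plausibly rise under usual care as well. The documents do not say by how much.

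Three ways of running the comparison fit the text, and each fails for the same reason:

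- **By arm.** One significant and one non-significant p-value do not compare the arms, and the arm three times larger has far more power to detect the same change.
- **Pooled.** The result is an uncontrolled change in a sample of which 30/40 = 75% use SweetMama.
- **SweetMama users only.** The result is a before-after p-value that ignores the randomised control.

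At stake is how two secondary questionnaires are read. The pilot is meant to inform a full trial that assesses behavior among other outcomes, and Potential Benefits anticipates gains in knowledge, motivation or engagement. A significant before-after change would look like confirmation of that, whether or not SweetMama contributed.

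**Working it through.** The plan gives no power or effect-size figure to reproduce. The check asks how often the by-arm reading would produce a misleading contrast if SweetMama had no effect on the measure.

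**Inputs from the documents**
- Target 40 at 1:3: 40 × 3/4 = 30 SweetMama and 40 × 1/4 = 10 usual care.
- Two-sided alpha of 0.05.
- The 80% target ("Feasibility targets for study retention will be set at 80% retention in the study protocol"), if met equally in both arms: 30 × 0.8 = 24 and 10 × 0.8 = 8.
- Maximum 50: about 37 and 13.

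**Assumptions**
- The true change is the same in both arms, in units of the SD of change (d), and is varied from 0 to 1.5.
- Change scores are normal with equal SD in both arms, and the arms are independent.
- One measure is taken at a time.

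**Formulas**
- Paired t-test power in an arm of size n comes from the noncentral t with n − 1 degrees of freedom and noncentrality d√n, against the critical value t(0.975, n − 1).
- P(pattern) = P(SweetMama significantly improved) × [1 − P(usual care significant)].

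**Example at d = 0.5**
- SweetMama, n = 30: noncentrality 0.5 × √30 = 2.74, power 0.754.
- Usual care, n = 10: noncentrality 0.5 × √10 = 1.58, power 0.293.
- SweetMama significant, usual care not: 0.754 × (1 − 0.293) = 0.533.
- Reverse: 0.293 × (1 − 0.754) = 0.072.

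**Range, 30 vs 10**

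| Shared change d | Power, SweetMama | Power, usual care | SweetMama significant, usual care not | Reverse |
|---|---|---|---|---|
| 0 | 5% | 5% | 2.4% | 2.4% |
| 0.1 | 8% | 6% | 7% | 4% |
| 0.2 | 18% | 9% | 17% | 7% |
| 0.3 | 36% | 14% | 31% | 9% |
| 0.5 | 75% | 29% | 53% | 7% |
| 0.8 | 99% | 62% | 38% | 0.7% |
| 1.0 | >99% | 80% | 20% | <0.1% |
| 1.2 | >99% | 92% | 8% | <0.1% |
| 1.5 | >99% | 99% | 1% | <0.1% |

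The maximum is 54%, near d = 0.55. The pattern exceeds 30% for d from about 0.30 to 0.88. In the d = 0 row, power is the two-sided rejection rate, and the pattern counts only significant improvement.

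**Other sample sizes**
- 24 vs 8: 26% at 0.3, 50% at 0.5, 49% at 0.8, 32% at 1.0.
- 37 vs 13: 36% at 0.3, 52% at 0.5, 25% at 0.8.
- 20 vs 20: both arms have the same power p, so each direction has probability of about p(1 − p), at most 0.5 × 0.5 = 25%.

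**Why the arms differ.** Significance needs an observed change of t/√n SDs: 2.045/√30 = 0.37 in SweetMama and 2.262/√10 = 0.72 in usual care.

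**Direct comparison.** In 50,000 simulated trials per scenario with identical true change, a two-sample t-test on change scores (10 vs 30) gave a false difference in 4.7% to 5.2% of trials for d from 0 to 0.8. Of the trials showing the misleading pattern at d = 0.5, about 4% also had a significant between-arm difference. Power is modest: by normal approximation, 28% for a true between-arm difference of 0.5 SD, 59% for 0.8 SD and 78% for 1.0 SD.

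**The case against.** The strongest reply is that the valid comparison is already planned. Part (b) of the sentence compares groups on behavioral measures, regression follows, and nothing says that within-person p-values will be used to make a claim for SweetMama. The study also calls itself non-hypothesis-testing, DES-SF and PAM are secondary, and neither 80% feasibility target depends on them. This stands to the extent that the defect is one of inference and reporting, not of a missing comparison. It does not remove the defect. The same Analysis text applies a significance threshold to all tests, and part (b) is not tied to change or to baseline.

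A reader might infer several stronger things that the documents do not support:

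- **That the plan tests each arm separately and will contrast the p-values.** The text does not say so. If the comparison is pooled or confined to SweetMama users, the two-p-value pattern cannot arise.
- **That the pattern will be common.** This depends on an unstated shared change. Below about 0.3 SD or above about 0.9 SD it falls under 30%, to 2.4% at no change and 1% at 1.5 SD.
- **That the 3:1 ratio alone produces it.** With no shared change the 3:1 figure is 2.4%, and equal arms can still give up to 25% in each direction. The ratio makes the pattern more frequent and one-sided when there is a shared change of moderate size.
- **That regression to the mean would raise the scores.** Eligibility does not select on DES-SF or PAM, so the documents give no ground to expect a shift in the mean from that source.

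**Conclusion.** The concern holds in a limited form. However it is run, the within-individual comparison is uncontrolled and supports no statement about SweetMama. The plan neither labels it descriptive nor specifies the between-group comparison of DES-SF and PAM in terms of change or baseline.

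The size is conditional. Under the by-arm reading at 30 vs 10, a shared change of roughly 0.3 to 0.9 SD yields the misleading contrast in about 30% to 54% of trials, against 7% for the reverse at 0.5 SD. Outside that range it is less common. These figures rest on the assumptions listed above, chiefly an equal true change that the documents neither state nor rule out. Looking at both DES-SF and PAM would raise the chance of seeing the pattern at least once.

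This is a worthwhile low-cost correction to a secondary analysis. It does not bear on retention, satisfaction or the feasibility targets.

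**What to change.** In the Quantitative paragraph of the pilot RCT analysis:

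1. State that within-arm change in DES-SF and PAM from baseline to postpartum will be reported as the mean change with 95% CI, separately by arm, as description and without p-values.
2. State that any statement about SweetMama on these measures will rest only on the between-arm difference with its 95% CI. The preferred form is the postpartum value compared between arms with adjustment for its baseline value. The difference in mean change is an acceptable alternative.

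The change needs a sentence or two and no new data, because both measures are already collected in all women at both times. The downside is the loss of a within-person p-value on secondary outcomes. The between-arm interval will be wide with 10 women in usual care, and it should be reported as such.

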# The objectives are to:

- Develop SweetMama and optimize its functionality through laboratory and field usability testing.
- Optimize SweetMama for patient preferences and satisfaction.

• Determine SweetMama feasibility; prepare for and conduct a pilot randomized controlled trial (RCT) comparing SweetMama use to standard of care.

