- Interview Semi-structured interview framed by the Health Belief Model on experiences with SweetMama. Information will be designed to elicit feedback about technical problems, ease of use, satisfaction and overall usefulness for various components of SweetMama (see Appendix D)
- System Usability Scale (SUS) A simple and technologically flexible 10-item scale to assess satisfaction with and usability of a product or service. 73,74
- Usefulness, Satisfaction and Ease of Use (USE) Questionnaire A 30-item scale to evaluate user interfaces across the three domains of usability, satisfaction, and perceived ease.

Specific user interaction data (regarding study retention and interactivity) also will be gathered via the SweetMama provider research platform, including:

Summary client events: number of times and days app was accessed, total usage length from first to last
access, number of times used per week, number of episodes of active use (defined as use from 1-20
minutes), average length of active use, total number of messages viewed, total number of messages
responded to, total number of messages "favorited", total number of individual goal messages received
and achieved, total number of self-initiated access events (i.e., not triggered by a routine message).

- Curriculum events (per message): time interval from sending message to participant viewing, dynamic
  option chosen, action taken with a follow-up message (i.e., was a link or phone number used after being
  provided), identification of favorite messages, and number of times messages in archive were viewed.
- Goal-setting events: specific goal content, dynamic option chosen, total time from message delivery to response, cumulative goal achievement, number of favorited and archived goal messages.

Only data related to how and when SweetMama is used will be collected and the format in which it is stored will contain no identifying information about users. Furthermore, the information saved on the server will only be accessible to people provided with the proper credentials (members of the research team, research collaborators, and the users themselves).

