- Individual testing: Analysis of individual data will consist of qualitative and quantitative analyses with the goals of identifying user feedback to incorporate participant needs into design and determining user features associated with greater satisfaction and use. The primary outcome will be user adherence, based on user interactivity data. Given the small study size and aim of assessing usability, the analysis of user interactivity data will be largely descriptive (i.e., no comparison group) but we will also examine the effects of potential mediating factors, such as health literacy and self-efficacy.

Secondary outcomes include both qualitative interview data and the quantitative data regarding use and patient characteristics, as described above. Qualitative data will be analyzed in the same manner as described above, with an additional mixed methods evaluation of interview data in concert with quantitative measures. Quantitative results for the SUS and USE will be used to assess satisfaction with and usability of SweetMama. User interaction data will be quantified to ensure tool functionality and determine areas for improvement. Using Stata v.15, we will perform bivariable and multivariable analyses to measure the relationships between baseline demographic/clinical characteristics, DES-SF, and PAM with user satisfaction and SweetMama interactivity.

- Provider surveys (in pilot RCT): Provider surveys will be analyzed using descriptive statistics as needed.
   We will analyze provider perceptions of engagement via the CSPAM and the modified CSPAM questions about SweetMama.
- Pilot RCT phase:
  - Qualitative and mixed methods: Exit interviews will use qualitative techniques and behavioral theories described above. We will use Dedoose software to perform a mixed methods analysis of themes in the context of quantitative measurements. For example, we will analyze satisfaction-related themes stratified by user interaction data such as quantity of episodes of active use, a measure of intervention exposure. This method allows us to assess several specific questions, such as if there are differences based on gestational age at enrollment or "dose" of intervention received.

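### The pilot's retention regression defines neither SweetMama use nor length of exposure; if use is a running total, an association with retention appears without any effect

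*Combined protocol and SAP*

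**What the plan says.** The relevant text is the quantitative paragraph for the pilot RCT phase, in the Analysis part of Data and Specimen Management (current protocol). It plans two analyses of retention:

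- a comparison "between groups (retention, behavioral measures and clinical outcomes";
- a regression to "assess the relationship of SweetMama use to retention and other behavioral outcomes", fitted "after controlling for potential confounders, such as length of exposure".

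The paragraph gives no variable, scale or time window for use. It does not say whether length of exposure is planned or actual time, and it does not name randomised arm as the regressor.

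Elsewhere the wording points both ways. The objectives describe a pilot to "conduct a pilot randomized controlled trial (RCT) comparing SweetMama use to standard of care", where use stands for the arm. The qualitative part of the same analysis section refers to "quantity of episodes of active use, a measure of intervention exposure". The interaction data listed under individual usability testing, which the pilot collects in identical form, include "number of times and days app was accessed, total usage length from first to last access".

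In the control arm, "Women who are randomized to usual care will receive no orientation to or enrollment in SweetMama". Retention is defined as staying in the study protocol. After a woman withdraws, no more prospective data are collected on her.

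**The concern.** If use is logged activity summed over follow-up, exposure and outcome share a clock. A woman's total stops growing when she leaves, so leavers have low totals because they left. A positive coefficient would then say nothing about whether the app keeps women in the study.

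Retention of at least 80% is the plan's feasibility criterion, and the pilot is meant to inform a full trial. This regression is also the only adjusted retention model described, and the analysis section treats p<0.05 as significant. A built-in association reported beside the comparison by arm could be taken as evidence of benefit when the larger trial is designed.

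**Working it through.** The plan gives no effect size or power figure for this analysis, so there is no figure to reproduce. The check has two parts.

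**1. Size of the built-in difference**

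- Planned participation, from Study Timelines: longest (40 − 6) + 10 = 44 weeks; shortest (40 − 30) + 10 = 20 weeks.
- Assumption: planned length uniform on 20-44 weeks, so the mean is (20 + 44)/2 = 32 weeks.
- Assumption: leavers go at a uniformly random point, so their mean time on study is 32 × 0.5 = 16 weeks.
- Assumption: 2 sessions a week, independent of leaving. Expected totals are 2 × 32 = 64 for women retained and 2 × 16 = 32 for leavers, a ratio of 2 with no effect of use.

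**2. False-positive rate under the null**

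From the protocol: target 40 at 1:3, so 40 × 1/4 = 10 usual care and 40 × 3/4 = 30 SweetMama; two-sided 0.05.

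Assumed, because the protocol gives no values: retention 70%, 80% or 90%, equal in both arms; uniform drop-out times; mean 1, 2 or 4 sessions a week, varying between women as a gamma with shape 2, plus shapes 1 and 5 at 2 sessions a week. About 1,500 trials were run per scenario. The Monte Carlo standard error near 44% is √(0.44 × 0.56/1500) = 0.013.

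Unadjusted comparisons within the SweetMama arm used Mann-Whitney tests. The adjusted and all-40 analyses used linear models of retention on use. The arm comparison used Fisher's exact test or a linear model.

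| Exposure | 80% retention, shape 2 | 80% retention, all use patterns | 70-90% retention, all use patterns |
|---|---|---|---|
| Randomised arm | 2-4% | 2-4% | 1-5% |
| Total use, SweetMama arm, unadjusted | 42-44% | 27-63% | 16-74% |
| Total use, SweetMama arm, adjusted for planned length | 28-30% | 12-61% | 4-72% |
| Total use, all 40 women, unadjusted | about 16% | 7-32% | 1-45% |
| Share of planned weeks with any use, SweetMama arm | 61-93% | 58-93% | 30-99% |
| Total use, adjusted for actual time on study | 2-3% | 2-3% | 1-5% |
| Rate per week on study, SweetMama arm | 4-6% | 4-6% | 4-6% |
| Use in first 4 weeks, SweetMama arm | 4-6% | 4-6% | 3-6% |

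The result depends on the scale of use. Totals, and the share of planned weeks with any use, carry the artefact; a rate while on study does not. Including the 10 usual-care women, who all have zero use, dilutes it. At 90% retention with the most variable use it disappears from the all-40 analysis (1%) and from the analysis adjusted for planned length (4%).

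The 4-week row assumes that the window is complete for every SweetMama woman. The simulations concern retention only, not the behavioural scales.

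**The case against.** The case for leaving the text alone has three parts.

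*Use may simply mean the arm.* The objectives use the phrase that way. The Background uses nearly the same wording for the future trial on perinatal outcomes. The sentence after the regression turns to the experimental group alone, which suggests that the regression itself covers both arms. This is a fair reading, so a reader who infers that the plan certainly regresses retention on logged activity goes further than the text. It is not the only reading, however: the analysis section also uses dose language, and length of exposure is an odd confounder for a randomised arm. Usual-care women have no app exposure, so for them it is zero, undefined or time on study. The arm reading therefore needs the covariate rewritten too.

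*The plan already adjusts for length of exposure.* If that means actual time on study, the artefact goes. But the covariate is then post-randomisation and nearly identical to retention, so the coefficient says little about retention. If it means planned time, much of the artefact usually remains.

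*A comparison of retention between groups is already planned.* It is, and a reader might wrongly infer that the regression replaces it. The regression stands beside it. The study also calls itself non-hypothesis-testing, and the 80% retention criterion does not depend on this model. Both points limit the consequences; neither makes the regression interpretable.

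**Conclusion.** The concern holds in a conditional form. The exposure and its main covariate are undefined, and one reading that the protocol supports gives a biased retention result. If use is a cumulative total, a null effect would be declared significant in roughly 30-45% of trials within the SweetMama arm and in about 16% using all 40 women unadjusted, against 2-4% by randomised arm. These figures assume 80% retention in both arms, uniform drop-out times and gamma-distributed weekly use with shape 2; the table shows how far they move. That stayers log larger totals is less sensitive to these assumptions, provided use is a running total and does not itself fall with longer stay.

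A reader might conclude that the analysis will report that SweetMama promotes retention. The documents do not support this: the scale of use is not fixed, some plausible scales are unbiased, and even under the total-use reading the false finding is far from certain.

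One related point needs reconciling. Loss to follow-up is defined by missed check-ins for any pilot participant, but check-ins are described only for SweetMama users. Naming the arm as the exposure does not settle whether retention is ascertained alike in both arms.

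**What to change.** In the quantitative paragraph for the pilot RCT phase:

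- Name randomised arm as the exposure in the regression of retention and behavioural outcomes, and state that all randomised women are analysed as allocated.
- Replace length of exposure with baseline covariates only: diabetes type, which is the stratification factor, and gestational age at entry.
- If use is to be related to retention, do so within the SweetMama arm and label it exploratory and non-causal. Measure use in a fixed early window, for example the first 4 weeks, and count retention afterwards among women still in the study at the end of that window.

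This is a wording change. The interaction data already planned, including "number of times and days app was accessed" and message-level timing, should supply the early-window measure. What is lost is a dose-response analysis based on use over the whole of follow-up, which would be dropped or reported as description only.
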